#### 4. STUDY DRUG

Study drug includes both Investigational [Medicinal] Product (IP/IMP) and Non-investigational [Medicinal] Product (Non-IP/Non-IMP) and can consist of the following:

**Table 4-1: Study Drugs for CA209714**

Product Description / Class and Dosage Form	Potency	IP/ Non-IMP	Blinded or Open Label	Packaging / Appearance	Storage Conditions (per label)
BMS-936558-01 (Nivolumab) Solution for Injection	100 mg (10 mg/mL)	IP	Open-label a	10 mL/vial (5 or 10 vials/carton)	Store at 2° - 8°C. Protect from light and freezing.
Ipilimumab Solution for Injection	200 mg (5 mg/mL)	IP	Open-label a	40 mL/vial (4 vials/carton)	Store at 2°- 8°C. Protect from light and freezing.
0.9% Sodium Chloride for Injection	N/A	IP	Open-label a	Various (local commercial product)	As per package insert
5% Dextrose for Injection	N/A	IP	Open-label a	Various (local commercial product)	As per package insert

a The term "open label" refers to the medication as it is upon receipt at the pharmacy. The trial will be conducted in a double-blinded fashion

Premedications or medications used to treat infusion-related reactions should be sourced by the investigative sites if available and permitted by local regulations. Solutions used as diluent or placebo (ie, 0.9% Sodium Chloride Injection or 5% Dextrose Injection) should also be sourced by investigative sites if available and permitted by local regulations.

##### 4.1 Investigational Product

An investigational product, also known as investigational medicinal product in some regions, is defined a pharmaceutical form of an active substance or placebo being tested or used as a reference in a clinical study, including products already with a marketing authorization but used or assembled (formulated or packaged) differently than the authorized form, or used for an unauthorized indication, or when used to gain further information about the authorized form.

The investigational product should be stored in a secure area according to local regulations. It is the responsibility of the investigator to ensure that investigational product is only dispensed to study subjects. The investigational product must be dispensed only from official study sites by authorized personnel according to local regulations.

- Nivolumab
- Ipilimumab
- Placebo for ipilimumab (0.9% sodium chloride injection or 5% dextrose injection)

#### **4.2 Non-investigational Product**

Other medications used as support or escape medication for preventative, diagnostic, or therapeutic reasons, as components of the standard of care for a given diagnosis, may be considered as non-investigational products.

#### **4.3 Storage of Study Drug**

The product storage manager should ensure that the study drug is stored in accordance with the environmental conditions (temperature, light, and humidity) as determined by BMS. If concerns regarding the quality or appearance of the study drug arise, the study drug should not be dispensed and contact BMS immediately.

Study drug not supplied by BMS will be stored in accordance with the package insert.

Investigational product documentation (whether supplied by BMS or not) must be maintained that includes all processes required to ensure drug is accurately administered. This includes documentation of drug storage, administration and, as applicable, storage temperatures, reconstitution, and use of required processes (eg, required diluents, administration sets).

Infusion-related supplies (eg, IV bags, in-line filters, 0.9% sodium chloride injection, 5% dextrose injection) will not be supplied by the sponsor and should be purchased locally if permitted by local regulations.

Please refer to the current version of the Investigator Brochure (IB) and/or pharmacy reference sheets for complete storage, handling, dispensing, and infusion information for nivolumab, ipilimumab, and matching placebo.

The unblinded pharmacist will obtain treatment assignment by interactive voice response system (IVRS) and prepare blinded drug.

Please refer to [Section 9.2](#) for guidance on IP records and documentation.

#### **4.4 Method of Assigning Subject Identification**

After the subject's initial eligibility is established and informed consent has been obtained, the subject must be enrolled into the study by an IVRS to obtain the subject number. Every subject that signs the informed consent form must be assigned a subject number in IVRS. Specific instructions for using IVRS will be provided to the investigational site in a separate document. The

investigator or designee will register the subject for enrollment by following the enrollment procedures established by BMS. The following information is required for enrollment:

- Date that informed consent was obtained
- Date of birth
- Gender at birth

Once enrolled in IVRS, enrolled subjects that have met all eligibility criteria will be ready to be randomized through IVRS. PD-L1 expression data will be transferred directly from analyzing lab to IVRS. The local HPV p-16 result will be entered by the site directly into IVRS for the oropharyngeal cancer and unknown primary with p-16 positive subjects during the randomization call. The following information is required for subject randomization:

- Subject number
- Date of birth
- HPV p-16 status (oropharyngeal HPV p-16 pos vs oropharyngeal HPV p-16 neg or nonoropharyngeal)
- Oropharyngeal CA sites defined in [Appendix 5](#)
- Tumor Cell PD-L1 expression status at 1% cutoff: (expressing/non-expressing/non-evaluable/indeterminate)
- Positive ( $\geq 1\%$  expressing) vs Negative ( $< 1\%$  expressing)/not evaluable/indeterminate)
- Platinum refractory subgroup status (yes vs no)

Subjects meeting all eligibility criteria will be stratified by PD-L1 status (expressing vs nonexpressing/non-evaluable/indeterminate), HPV p-16 status (oropharyngeal HPV p-16 positive vs oropharyngeal HPV p-16 negative/non-oropharyngeal) and platinum refractory subgroup status (yes vs no). Subjects will be randomized in a 2:1 ratio to nivolumab + ipilimumab (Arm A) vs nivolumab + ipilimumab-placebo (Arm B).

Enrollment will stop once approximately 396 subjects have been randomized.

The exact procedures for using the IVRS will be detailed in the IVRS manual.

#### **4.5 Selection and Timing of Dose for Each Subject**

The dosing schedule is detailed below in [Section 4.5.1](#).

All subjects will be monitored continuously for AEs while on study treatment. Treatment modifications (eg, dose delay, interruption, discontinuation) will be based on specific laboratory and adverse event criteria, as described in [Sections 4.5.2, 4.5.3, 4.5.4 and 4.5.5](#).

### 4.5.1 Dosing

**Table 4.5.1-1: Study Drugs for CA209714**

	Cycle 1 Day 1 ± 3 Days	Cycle 1 Day 15 ± 3 Days	Cycle 1 Day 29 ± 3 Days
Arm A: a Nivolumab 3 mg/kg q 2 weeks + Ipilimumab 1 mg/kg q 6 weeks a	Nivolumab + Ipilimumab	Nivolumab	Nivolumab
Arm B: b Nivolumab 3 mg/kg q 2 weeks + Ipi-placebo 1 mg/kg q 6 weeks b	Nivolumab + Ipilimumab-placebo	Nivolumab	Nivolumab

a Arm A: Both nivolumab and ipilimumab should be administered as 30 minute infusions. nivolumab is to be administered first. The second infusion will be ipilimumab and will start at least 30 minutes after completion of the nivolumab infusion

b Arm B: Both nivolumab and ipilimumab-placebo should be administered as 30 minute infusions. nivolumab is to be administered first. The second infusion will be ipilimumab-placebo and will start at least 30 minutes after completion of the nivolumab infusion

#### 4.5.1.1 Nivolumab plus Ipilimumab or ipilimumab-placebo

Subjects are randomized to receive treatment with nivolumab as a 30 minute infusion 3 mg/kg every 2 weeks (± 3 calendar days) and ipilimumab or ipilimumab-placebo as a 30 minute infusion 1 mg/kg every 6 weeks (± 3 calendar days), but no less than 12 days of the previous dose starting on Day 1, until progression, unacceptable toxicity, withdrawal of consent, 24 months from the first dose of treatment, or the study ends, whichever occurs first.

When study drugs (nivolumab and ipilimumab) are to be administered on the same day, nivolumab is to be administered first and separate infusion bags and filters should be used for each infusion. Nivolumab infusion must be promptly followed by a flush of diluent to clear the line of nivolumab before starting the ipilimumab infusion. The second infusion will always be the ipilimumab study drug and will start after the infusion line has been flushed, filters changed, and subject has been observed to ensure no infusion reaction has occurred. The time in between infusions is expected to be at least 30 minutes. Nivolumab and ipilimumab or ipilimumab-placebo may be diluted in 0.9% Sodium Chloride Solution or 5% Dextrose solution.

Dosing calculations should be based on the body weight. If the subject's weight on the day of dosing differs by > 10% from the weight used to calculate the prior dose, the dose must be recalculated. Doses can be rounded per institutional standards. There will be no dose escalations or reductions of nivolumab and ipilimumab or ipilimumab-placebo allowed.

Subjects may be dosed with nivolumab no less than 12 days from the previous dose. There are no premedications recommended. Subjects may be dosed with Ipilimumab or Ipilimumab-placebo no less than 6 weeks from the previous dose.

Doses of nivolumab and/or ipilimumab or ipilimumab-placebo may be interrupted, delayed, or discontinued depending on how well the subject tolerates the treatment. For more details, see Sections 4.5.2 (dose delays), 4.5.4 (resuming treatment), and 4.5.5 (discontinuation).

## **4.5.2 Dose Delays**

### **4.5.2.1 Nivolumab and Ipilimumab/ipilimumab-placebo**

Dose delay criteria apply for all drug-related AEs. Treatment delay up to 6 weeks for nivolumab and up to 12 weeks for ipilimumab or ipilimumab-placebo from the last dose are allowable (any dose delays greater than these will require approval from the medical monitor).

Tumor assessments for all subjects should continue as per protocol even if dosing is delayed. Nivolumab and ipilimumab or ipilimumab-placebo administration should be delayed for the following:

- Any Grade 2 non-skin, drug-related adverse event, except of fatigue
- Any Grade 2 drug-related creatinine, AST, ALT, and/or Total Bilirubin abnormalities
- Grade 3 skin, drug-related AE
- Any Grade 3 drug-related laboratory abnormality with the following exceptions:
  - Grade 3 lymphopenia or asymptomatic amylase or lipase does not require dose delay
  - Grade  $\geq 3$  AST, ALT, total bilirubin will require dose discontinuation (see Section 4.5.5)
- Any AE, laboratory abnormality, or intercurrent illness which, in the judgment of the investigator, warrants delaying the dose of study medication.
- Subjects receiving ipilimumab or ipilimumab-placebo in combination with nivolumab that have drug-related toxicities that meet the criteria for dose delay, should have both drugs (ipilimumab or ipilimumab-placebo and nivolumab) delayed until retreatment criteria are met. (Exceptions apply to the retreatment criteria after dose delay of ipilimumab or ipilimumab-placebo and nivolumab for Grade  $\geq 3$  amylase and lipase abnormalities that are not associated with symptoms or clinical manifestations of pancreatitis and that are attributed to ipilimumab or ipilimumab-placebo alone.)

#### Rescheduling:

- Nivolumab may be delayed until the next planned ipilimumab or ipilimumab-placebo dose if the next ipilimumab or ipilimumab-placebo dose is scheduled within the next 12 days. This will permit periodic ipilimumab or ipilimumab-placebo dosing to be synchronized with nivolumab dosing.
- Ipilimumab or ipilimumab-placebo should be dosed at the specified interval regardless of any delays in intervening nivolumab doses. However, in order to maintain periodic synchronized dosing of ipilimumab or ipilimumab-placebo and nivolumab, the dosing days of nivolumab and ipilimumab or ipilimumab-placebo may be adjusted within the permitted  $\pm 3$  day window, as long as consecutive nivolumab doses are given at least 12 days apart. Ipilimumab may be delayed beyond the 3 day window if needed to synchronize with the next nivolumab dose.

- If an ipilimumab or ipilimumab-placebo dose is delayed beyond 6 weeks from the prior ipilimumab or ipilimumab-placebo dose, then subsequent ipilimumab or ipilimumab-placebo doses should be rescheduled to maintain the 6 week interval between consecutive ipilimumab or ipilimumab-placebo doses.
- A dose delay of ipilimumab or ipilimumab-placebo which results in no ipilimumab or ipilimumab-placebo dosing for > 12 weeks requires ipilimumab or ipilimumab-placebo discontinuation, with exceptions as noted in [Section 4.5.5.2](#).

Participants who require delay of nivolumab should be re-evaluated weekly or more frequently if clinically indicated and resume nivolumab dosing when re-treatment criteria are met.

#### **4.5.3 Dose Reductions**

##### **4.5.3.1 Nivolumab or Ipilimumab/ipilimumab-placebo**

There will be no dose reductions for nivolumab or ipilimumab or ipilimumab-placebo allowed.

#### **4.5.4 Criteria to Resume Treatment**

##### **4.5.4.1 Criteria to Resume Nivolumab Treatment**

Subjects may resume treatment with nivolumab when the drug-related AE(s) resolve(s) to Grade ≤ 1 or baseline, with the following exceptions:

- Subjects may resume treatment in the presence of Grade 2 fatigue.
- Subjects who have not experienced a Grade 3 drug-related skin AE may resume treatment in the presence of Grade 2 skin toxicity.
- For subjects with Grade 2 AST/ALT and/or total bilirubin values, dosing may resume when laboratory values return to baseline and management with corticosteroids, if needed, is complete.
- Drug-related pulmonary toxicity, diarrhea, or colitis must have resolved to baseline before treatment is resumed. Subjects with persistent Grade 1 pneumonitis after completion of a steroid taper over at least 1 month may be eligible for retreatment if discussed with and approved by the BMS Medical Monitor.

Subjects with drug-related endocrinopathies adequately controlled with only physiologic hormone replacement may resume treatment after consultation with the BMS Medical Monitor (or designee). Adrenal insufficiency requires discontinuation regardless of control with hormone replacement.

##### **4.5.4.2 Criteria to Resume Ipilimumab/ipilimumab-placebo Dosing**

Subjects may resume treatment with nivolumab and ipilimumab or ipilimumab-placebo when drug-related AE(s) resolve(s) to Grade 1 or baseline value, with the following exceptions:

- Subjects may resume treatment in the presence of Grade 2 fatigue.
- Subjects who have not experienced a Grade 3 drug-related skin AE may resume treatment in the presence of Grade 2 skin toxicity.

- Subjects with baseline Grade 1 AST/ALT or total bilirubin who require dose delays for reasons other than a 2-grade shift in AST/ALT or total bilirubin may resume treatment in the presence of Grade 2 AST/ALT or total bilirubin.
- Subjects with combined Grade 2 AST/ALT and total bilirubin values meeting discontinuation parameters ([Section 4.5.5.2](#)) should have treatment permanently discontinued.
- Drug-related pulmonary toxicity, diarrhea, or colitis must have resolved to baseline before treatment is resumed.
- Subjects who received systemic corticosteroids for management of any drug-related toxicity must be off corticosteroids or have tapered down to an equivalent dose of prednisone  $\leq 10$  mg/day.
- Drug-related endocrinopathies adequately controlled with only physiologic hormone replacement may resume treatment after consultation with the BMS Medical Monitor.
- Dose delay of ipilimumab or ipilimumab-placebo which results in no ipilimumab or ipilimumab-placebo dosing for  $> 12$  weeks requires ipilimumab or ipilimumab-placebo discontinuation, with exceptions as noted in [Section 4.5.5.2](#).
- Ipilimumab may not be resumed sooner than 6 weeks ( $\pm 5$  days) after the prior ipilimumab or ipilimumab-placebo dose.
- In general, subjects who meet criteria to resume ipilimumab or ipilimumab-placebo will also have met criteria to resume nivolumab, so it should be feasible to synchronize dosing of both drugs when resuming ipilimumab or ipilimumab-placebo. In order to facilitate this, the dosing days of nivolumab and ipilimumab or ipilimumab-placebo may be adjusted within the permitted  $\pm 5$  day window, as long as consecutive nivolumab doses are given at least 12 days apart.
- One exception to note is when ipilimumab or ipilimumab-placebo and nivolumab doses are delayed due to drug-related Grade  $\geq 3$  amylase or lipase abnormalities not associated with symptoms or clinical manifestations of pancreatitis. If the investigator assesses the Grade  $\geq 3$  amylase or lipase abnormality to be related to ipilimumab or ipilimumab-placebo and not related to nivolumab, nivolumab may be resumed when the amylase or lipase abnormality resolves to Grade  $< 3$  but ipilimumab or ipilimumab-placebo may only be resumed when the amylase or lipase abnormality resolves to Grade 1 or baseline. Investigator attribution of this toxicity to the ipilimumab or ipilimumab-placebo dosing must be clearly noted in the subject's medical chart. The BMS Medical Monitor should be consulted prior to resuming nivolumab in such subjects.

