**Table 5.1-2: On Treatment Procedural Outline (CA209714)**

Procedure	Each Cycle Day1 ± 3	Each Cycle Day 15 ± 3	Each Cycle Day 29 ± 3	Notes
Safety Assessments				
Targeted Physical Examination	X	X	X	
Vital Signs	X	X	X	Including BP, HR, and temperature.
Physical measurements (including performance status)	X	X	X	Weight and ECOG status. The dosing calculations should be based on the body weight. If the subject's weight on the day of dosing differs by > 10% from the weight used to calculate the dose, the dose must be recalculated. All doses should be rounded to the nearest milligram.
Adverse Events Assessment	X	X	X	
Laboratory Tests	X	X	X	On-study local laboratory assessments should be done within 72 hours prior to each dose, CBC w/differential, (Albumin if clinically indicated), LFTs (ALT, AST, total bilirubin, alkaline phosphatase), BUN or serum urea level, creatinine, Ca, Mg, Na, K, Cl, LDH, phosphate, glucose, amylase, lipase, TSH with reflexive Free T4, Free T3.  (Thyroid Function Testing to be evaluated every 6 weeks)
Pregnancy Test (WOCBP only)		See note		Serum or urine within 24 hours prior to first dose and then every 4 weeks (± 1 week) regardless of dosing schedule.

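### For one liver scenario, Protocol 4.5.4.1 and 4.5.4.2 give opposite answers on restarting nivolumab, and no visible text says which governs

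*Protocol*

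**What the plan says.** Section 4.5.2.1 requires a delay for any drug-related Grade 2 AST, ALT or total bilirubin abnormality. Subjects whose toxicity meets the delay criteria "should have both drugs (ipilimumab or ipilimumab-placebo and nivolumab) delayed until retreatment criteria are met". The Rescheduling text in the same section tells sites to "resume nivolumab dosing when re-treatment criteria are met". Neither place names a subsection.

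Section 4.5.4.1 covers nivolumab. Its general rule is recovery to Grade 1 or lower, or to baseline. It then makes an exception after Grade 2 AST/ALT and/or total bilirubin: "dosing may resume when laboratory values return to baseline and management with corticosteroids, if needed, is complete".

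Section 4.5.4.2 is headed for ipilimumab/placebo, but its opening rule covers both drugs: "Subjects may resume treatment with nivolumab and ipilimumab or ipilimumab-placebo when drug-related AE(s) resolve(s) to Grade 1 or baseline value". Three of its bullets bear on liver values or on recovery to baseline:

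- One concerns "Subjects with baseline Grade 1 AST/ALT or total bilirubin who require dose delays for reasons other than a 2-grade shift" in those values.
- One requires permanent discontinuation when combined AST/ALT and bilirubin values meet the discontinuation limits.
- One requires return to baseline for pulmonary toxicity, diarrhea and colitis. It does not list liver values.

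A further bullet says that subjects given systemic steroids for a drug-related toxicity "must be off corticosteroids or have tapered down to an equivalent dose of prednisone" of 10 mg/day or less.

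**The concern.** Every subject is assigned both infusions, and 4.5.2.1 encourages sites to synchronize them. A site deciding on a joint restart will naturally turn to 4.5.4.2, because it is the section that mentions both drugs. If the site uses that list alone, it can restart nivolumab together with ipilimumab or placebo at a liver value at which 4.5.4.1 says nivolumab must wait.

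Applied separately, the two sections also give an odd ordering. With identical laboratory values, a nivolumab-only visit would need return to baseline, while a visit at which ipilimumab/placebo is also due would accept Grade 1. Nothing visible explains a looser liver threshold for the combination.

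What is at stake is liver safety for individual subjects and consistency of dosing decisions between sites.

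**Working it through.** The plan gives no figure on this point and no arithmetic applies. The check applies each section to one case and then looks for a rule of precedence.

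**Test case.** Normal baseline; isolated drug-related Grade 2 AST/ALT or bilirubin, meaning not a combined elevation that meets the discontinuation limits; both drugs delayed; value now Grade 1; steroids never needed or finished.

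**Step 1: 4.5.4.1.** The general rule would accept Grade 1, but the liver exception replaces it with return to baseline. Grade 1 is above a normal baseline. Answer for nivolumab: wait.

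**Step 2: 4.5.4.2.** The opening rule accepts Grade 1 and names nivolumab. The first liver bullet applies only to subjects whose baseline was already Grade 1. The second applies only to combined values that meet the discontinuation limits. The return-to-baseline bullet does not mention the liver. The steroid condition is met. Answer for nivolumab with ipilimumab/placebo: may resume.

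**Step 3: neighbouring cases.**

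| Baseline | Current value | 4.5.4.1 | 4.5.4.2 |
|---|---|---|---|
| Normal | Normal | Resume | Resume |
| Normal | Grade 1 | Wait | Resume |
| Grade 1 | Grade 1 | Resume | Resume |

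With steroids out of the picture, these rows differ only where the value has improved to Grade 1 from Grade 2 but the baseline was normal.

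**Step 4: is there a tie-breaker?**

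- Sections 4.5 and 4.5.1.1 refer readers to 4.5.4 as a whole and do not rank its parts.
- Section 4.5.2.1, including its Rescheduling text, mentions restart criteria without saying which.
- The synchronization bullet in 4.5.4.2 says that subjects who qualify for ipilimumab will in general already qualify for nivolumab. In the test case they do not.
- The one exception flagged after that bullet concerns amylase and lipase only.
- The instructions in 4.5.5.1 and 4.5.5.2 to assess each drug separately concern discontinuation, not restarting.
- Section 4.5.6 refers to management algorithms in Appendix 2 and the Investigator Brochures. The hepatic algorithm is not visible in the public text.

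No express precedence was found in what can be read.

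**The case against.** The strongest reply is that the two sets of criteria are cumulative. The headings assign 4.5.4.1 to nivolumab and 4.5.4.2 to ipilimumab/placebo. The synchronization bullet treats the nivolumab criteria as a separate set that must itself be satisfied, and it would have little purpose if 4.5.4.2 alone could authorize nivolumab. The general pointers to 4.5.4 as a whole fit that reading. This argument largely stands: it is the better reading, and under it 4.5.4.1 controls and the conflict disappears. But a site has to infer it. The opening sentence of 4.5.4.2 points the other way, and the synchronization bullet reassures sites that the nivolumab criteria will usually be met already.

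The second reply is that Appendix 2 may contain the answer. That cannot be excluded, so the claim is limited to visible text.

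The third is that other safeguards limit any harm. "On-study local laboratory assessments should be done within 72 hours prior to each dose", and those tests include liver function. Under 4.5.2.1 the investigator may delay for any laboratory abnormality, and under 4.5.5.1 drug-related Grade 3 or higher values generally end nivolumab. These keep the point minor.

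Three stronger inferences are tempting, and the documents do not support them:

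- *The liver rule was deliberately left out of 4.5.4.2.* A reader might infer this because that section repeats other exceptions, for example "Drug-related pulmonary toxicity, diarrhea, or colitis must have resolved to baseline before treatment is resumed". But the sentence in 4.5.4.1 that follows it, on persistent Grade 1 pneumonitis, is not repeated either. The lists differ in more than the liver rule, and on pneumonitis 4.5.4.2 is the stricter.
- *The baseline-Grade-1 bullet lets a subject restart with a persisting Grade 2 liver event.* That bullet can equally be read as covering delays for a different toxicity.
- *The steroid conditions contradict each other.* That depends on whether completed steroid management in 4.5.4.1 means fully off steroids, which is not defined.

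**Conclusion.** The conflict is real but narrow. For a subject with a normal baseline, delayed for an isolated drug-related Grade 2 AST/ALT or bilirubin value and now at Grade 1, the literal text of 4.5.4.1 withholds nivolumab and the literal text of 4.5.4.2 permits it with ipilimumab/placebo. The cumulative reading is probably what was meant, but it is not stated.

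Severity is minor. The documents give no rate for this event, so no patient count can be attached. A reader might go on to infer that the protocol endorses unsafe restarts or that the trial's efficacy result is compromised. Neither follows: the likely intent is the stricter rule, the restart rules are the same in both blinded arms, and the alpha, the power and the ORR comparison do not depend on them. The conclusion rests on the visible text and would fall away if the Appendix 2 hepatic algorithm states which condition applies.

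**What to change.** Add one sentence to 4.5.4.2: after a delay for drug-related Grade 2 AST/ALT and/or total bilirubin, nivolumab, alone or with ipilimumab/placebo, may resume only when the liver condition of 4.5.4.1 is also met, that is, values back to baseline and any corticosteroid management complete. Keeping the sentence to Grade 2 events matches the scope of the existing 4.5.4.1 exception. The Appendix 2 hepatic algorithm should be checked for agreement at the same time.

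If the cumulative reading was intended, this changes no intended practice. The cost is a wording amendment and slightly longer holds for a few subjects. A hold of more than 6 weeks from the previous nivolumab dose would meet the existing discontinuation limit in 4.5.5.1. That section already exempts prolonged steroid tapers for drug-related events, but a value that stays at Grade 1 without a taper would not be covered by that exemption.
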